8.5.2 Analysis of the secondary variables

For the secondary efficacy endpoints, a Cochran-Mantel-Haenszel (CMH) test stratified by baseline HbA1c stratum ($<9.0\%$ or $\geq 9.0\%$) will be applied to the categorical variables, and an MMRM model or analysis of covariance (ANCOVA) model will be applied to the continuous variables.

The significance or non-significance of the treatment comparisons for the primary efficacy endpoint will determine whether or not the statistical tests are to be performed to compare treatments for the secondary efficacy endpoints. In other words, if and only if the superiority of the combination treatment group is established simultaneously over both the individual treatment groups in primary endpoint at 5% level of significance, only then can the analyses of the set of 7 secondary endpoints be performed at 5% level of significance. In order to control the overall type-I error rate at 5% level of significance, multiplicity adjustment will be applied while analyzing the set of secondary endpoints, details of which will be provided in the SAP prior to unblinding of treatment assignments.

The 7 secondary endpoints are listed below:

- Change in total body weight from baseline to Week 28
- Change in FPG from baseline to Week 28
- Change from baseline in 2-hour PPG after standardized MTT at Week 28
- Proportion of patients achieving HbA1c $<7.0\%$ at Week 28

- Proportion of patients achieving weight loss ≥ 5 .0% at Week 28
- Change from baseline in FPG to Week 2 (dapagliflozin+exenatide vs exenatide)
- Change from baseline in seated systolic BP from baseline to Week 28

Although the nominal p-values respective to each of the treatment comparisons for all the 7 secondary endpoints will be presented in the report, in order to control the overall type-I rate at 5% level of significance, multiplicity adjustment will be applied while performing the 13 treatment comparisons in the set of 7 secondary endpoints, details of which will be provided in the SAP prior to unblinding of treatment assignments.

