3.1 Inclusion criteria

For inclusion in the study patients should fulfill the following criteria:

1. Provision of informed consent prior to any study specific procedures.
2. Is able to read, understand, and sign the Informed Consent Forms (ICFs) and, if applicable, an Authorization to Use and Disclose Protected Health Information form (consistent with Health Insurance Portability and Accountability Act of 1996 [HIPAA] legislation), communicate with the investigator, and understand and comply with protocol requirements.
3. Is at least 18 years old at Screening; the upper age limit should be based on local metformin label restrictions.
4. Has a diagnosis of T2DM.
5. Has HbA1c of 8.0% to 12.0%, inclusive, at Visit 1 and Visit 2.
6. Treated with a stable dose of metformin 500 mg/day for at least 2 months prior to Screening.
7. Is male, or is female and meets all the following criteria:
 - Not breastfeeding.
 - Negative pregnancy test result (human chorionic gonadotropin, beta subunit [β hCG]) at Visit 1 (Screening) (not applicable to hysterectomized females).
 - If of childbearing potential (including perimenopausal women who have had a menstrual period within 1 year), must practice and be willing to continue to

practice appropriate birth control (defined as a method which results in a low failure rate, ie, less than 1% per year, when used consistently and correctly, such as implants, injectables, hormonal contraceptives [pills, vaginal rings, or patches], some intrauterine contraceptive devices [levonorgestrel-releasing or copper-T], tubal ligation or occlusion, or a vasectomized partner) during the entire duration of the study. As applicable, all methods must be in effect prior to receiving the first dose of study medication.

- Must practice appropriate birth control as stated above for 10 weeks after the last dose of study medication.

8. Patients who are receiving the following medications must be on a stable treatment regimen for a minimum of 2 months prior to Visit 1 (Screening):

- Antihypertensive agents
- Thyroid replacement therapy
- Antidepressant agents.

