3.5 Methods for assigning treatment groups

Patients who meet all criteria for this study will be randomized to double-blinded treatment at Visit 3. Assignment to treatment groups will be determined by a computer-generated random sequence using an IVRS. Random assignment to study treatment will be stratified by HbA1c stratum ($<9.0\%$ or $\geq 9.0\%$) based on the HbA1c (%) value of individual patients that was measured at a visit immediately preceding the randomization visit (which is Visit 2 at Week -1 in this study) and is available at the time of randomization. However, throughout the protocol, this is referred to as the baseline HbA1c stratum.

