8.2 Sample size estimate

A total of 209 patients per treatment group are required, assuming:

- Mean difference of 0.35% in HbA1c change from baseline with EQW + dapagliflozin versus each monotherapy
- Standard deviation of 1.1% and 90% power (based on a 2-sample t-test at a 0.05 significance level)

Assuming a 5% drop-out rate prior to Week 4 (Visit 6), the first visit where HbA1c is tested, 220 patients per treatment arm (a total of approximately 660 patients) would have post-baseline measurements of HbA1c and thus be included in the ITT analysis of the primary objective. Assuming 40% screen failure, a total of 1100 patients will be screened.

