8.4.2 Secondary efficacy endpoints

- Change in total body weight from baseline to Week 28
- Change in FPG from baseline to Week 28
- Change from baseline in 2-hour PPG after standardized MTT at Week 28
- Proportion of patients achieving HbA1c <7.0% at Week 28
- Proportion of patients achieving weight loss ≥ 5 .0% at Week 28
- Change from baseline in FPG to Week 2 (dapagliflozin+exenatide vs exenatide)
- Change from baseline in seated systolic BP from baseline to Week 28

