8.5 Methods for statistical analyses

8.5.1 Analysis of the primary variable

The primary analysis will assess the benefit (superiority) of the combination of EQW + dapagliflozin over the individual components (ie, over EQW and over dapagliflozin) for the change in HbA_{1c} from baseline to Week 28 of the short-term double-blind treatment period for the ITT population.

The mixed model for the repeated measures (MMRM) will include change from baseline to Week 28 in HbA_{1c} as the dependent variable, treatment, region, baseline HbA_{1c} stratum ($<9.0\%$ or $\geq 9.0\%$), week, and treatment by week interaction as fixed factors. Baseline measurement of HbA_{1c} will be included as a continuous covariate. All observed HbA_{1c} values from post-baseline (including early dropouts, but excluding those data points after glycemic rescue therapy or post-treatment follow-up) will be included in the MMRM analysis. Since MMRM will be used for the primary analysis of primary endpoint, there will be no need

to impute missing data. Consequently, no Last Observation Carried Forward or other imputation technique will be required or used for the primary analysis. An unstructured covariance matrix will be used for the MMRM analysis, unless the model does not converge, in which case the covariance structure will be decided based on model convergence status and the Akaike information criterion. The least-squares (LS) means, standard errors, and 2-sided 95% confidence intervals, as well as the mean difference between treatment groups (EQW + dapagliflozin compared to EQW and compared to dapagliflozin) will be presented.

The treatment comparison of the primary efficacy endpoint (HbA1c change from baseline) will be considered significant if and only if the comparisons of the combination treatment group (EQW + dapagliflozin) against both of the 2 active-control groups (dapagliflozin 10 mg QD and EQW 2 mg) are significant. Due to this specific criterion for showing superiority of the combination treatment group over the individual treatment groups in primary endpoint, no multiplicity adjustment for the primary analysis will be required to control the overall type-I error, which is considered to be 0.05; consequently, both of the individual treatment comparisons will be performed at 5% level of significance (ie, $\alpha = 0.05$ 2-sided).

The same MMRM analysis will be applied to the PP population as a supportive analysis for the primary efficacy endpoint.

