8.5.3 Analysis of exploratory variables

For categorical variables, a CMH test, stratified by baseline HbA1c stratum ($<9.0\%$ or $\geq 9.0\%$) will be applied to compare the differences between treatment groups.

For continuous variables, a MMRM or analysis of co-variance (ANCOVA) model will be applied to compare the differences between treatment groups.

Detailed analysis methodology for the exploratory efficacy endpoints will be provided in the SAP.

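### For HbA1c <7.0% at Week 28, the CMH test adjusts only for a two-level HbA1c split; adding continuous baseline HbA1c would be a cheap, small gain in power

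*Protocol*

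**What the plan says.** Protocol section 8.5.2 names the test for categorical secondary endpoints: "a Cochran-Mantel-Haenszel (CMH) test stratified by baseline HbA1c stratum" (<9.0% or >=9.0%). No other covariate is named for it. What that section leaves to the SAP is the multiplicity adjustment, not the choice of this test.

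Section 8.4.2 lists the endpoint concerned: "Proportion of patients achieving HbA1c <7.0% at Week 28". Section 8.5.2 counts 13 comparisons over 7 secondary endpoints. FPG at Week 2 is compared with exenatide only, and the other six endpoints have two comparisons each (6 x 2 + 1 = 13). HbA1c <7.0% therefore supplies 2 of the 13.

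The entry criterion in section 3.1 is "Has HbA1c of 8.0% to 12.0%, inclusive, at Visit 1 and Visit 2". HbA1c is measured again at Visit 3 (Table 1). For the primary MMRM, section 8.5.1 uses the stratum as a factor and adds: "Baseline measurement of HbA_{1c} will be included as a continuous covariate".

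The protocol gives no response rate, no power for any responder endpoint, no baseline HbA1c distribution, and no correlation between baseline and Week 28 HbA1c.

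**The concern.** The endpoint is a threshold on the same variable that is measured at baseline. To get below 7.0%, a patient at 8.0% must fall by more than 1.0 point, one at 9.0% by more than 2.0, and one at 12.0% by more than 5.0. Within the single >=9.0% stratum the required fall spans 3.0 points, or 3.0/1.1 = 2.7 times the SD of change assumed in section 8.2. Larger falls at higher baselines will offset part of this, but the CMH test ignores whatever difference remains within a stratum.

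The primary analysis takes up that within-stratum information through the continuous covariate, whereas the responder analysis does not. At stake is some power for two comparisons that can support confirmatory claims. The primary analysis and the sample size are not affected.

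**Working it through.** **The plan's own figure.** Normal approximation: n = 2(1.960 + 1.282)^2 x 1.1^2 / 0.35^2 = 208 per group. The exact two-sample t-test gives 209 (power 90.06%). Then 209/0.95 = 220 per arm and 660/(1 - 0.40) = 1100 screened. The figures in section 8.2 reproduce, but they concern the primary endpoint only.

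**Inputs from the protocol.** 209 evaluable patients per arm, difference 0.35%, SD of change 1.1%, entry range 8.0% to 12.0%, stratum cut at 9.0% on the Visit 2 value, responder = Week 28 HbA1c <7.0%, two-sided 0.05.

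**Assumptions, not in the protocol.** Baseline mean 9.3 and SD 1.0 (one scenario 9.0 and 0.8) before the entry limits are applied; within-patient visit SD 0.2; mean change on monotherapy -1.5; slope of change on baseline from 0 to -0.7; no missing data.

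**Data model.** Week 28 = B + change, where B is the Visit 3 value, T is 1 for the combination, and change = -1.5 - 0.35 T + slope x (B - mean B) + e. The SD of e is sqrt(1.1^2 - slope^2 x var(B)), so that the SD of change stays at 1.1.

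**Analyses compared in each simulated trial.**
- CMH over the two strata k: z = sum(a_k - n1k m1k/N_k) / sqrt(sum n1k n0k m1k m0k / (N_k^2 (N_k - 1))).
- Logistic: logit P = b0 + b1 T + b2 stratum + b3 (B - 9), Wald test of b1.
- Standardized: the mean over all patients of p(T=1) - p(T=0) from that model, with a robust SE using N minus the number of parameters as divisor.

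**Results (6,000 trials per row; one comparison at two-sided 0.05).**

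| Scenario (approx. correlation of baseline with Week 28) | Responders | CMH | Logistic | Standardized |
|---|---|---|---|---|
| slope 0 (0.6) | 33.0 vs 24.4% | 55.3% | 60.4% | 60.6% |
| slope -0.3 (0.5) | 30.5 vs 21.3% | 61.1% | 63.2% | 63.6% |
| slope -0.5 (0.4) | 28.4 vs 18.6% | 67.1% | 68.7% | 69.2% |
| slope -0.7 (0.25) | 25.5 vs 15.4% | 74.0% | 74.5% | 74.9% |
| mean 9.0, SD 0.8, slope -0.3 (0.4) | 39.7 vs 28.8% | 68.4% | 70.3% | 70.6% |
| no effect, slope -0.3 | 21.3 vs 21.2% | 5.2% | 5.0% | 5.1% |

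The logistic gains over CMH are 5.1, 2.1, 1.6, 0.5 and 1.9 points. The standardized gains are 5.3, 2.5, 2.1, 0.9 and 2.2. Monte Carlo error is about 0.6 points per power figure, and the comparisons are paired within trials.

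**Stricter level.** At 0.05/13 (an assumed Bonferroni level, since the adjustment is left to the SAP), the logistic gain runs from -0.8 to +2.7 points and the standardized gain from +1.6 to +4.1.

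**Two further simulations.**
- With four assumed regions in the model, CMH versus standardized power was 55.4 vs 61.1%, 64.6 vs 67.3%, 71.5 vs 73.0% and 79.2 vs 79.8% as baseline predicted less. Plain logistic changed power by -0.2 to +4.5 points. Null rejection was 5.3% for CMH and 5.9% for the standardized analysis, so part of that gain may come from a slightly small robust SE.
- With residual SD 1.0, visit noise SD 0.25 and no region (8,000 trials per scenario), power was 74.4 vs 75.7%, 71.1 vs 74.0%, 68.8 vs 71.7% and 66.5 vs 69.1%. Null rejection was 5.1% for both.

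**The case against.** The strongest reply is that nothing here is wrong. CMH stratified by the randomization factor is a valid, prespecified test with type I error near 5%. Exchanging a table-based p-value for a model-based one to gain about 2 points is close to a matter of preference. Section 8.5.2 also names no effect measure for responder endpoints, so a marginal risk difference would be an addition to the plan. All of this stands, and it limits the point to an optional improvement.

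The size is also open to challenge. The simulations have no missing data, although some patients will be rescued or drop out. At a multiplicity-adjusted level a plain logistic test can lose slightly, so the benefit there depends on the standardization step. These points stand too.

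A reader might infer more than the protocol supports in four ways:
- *That baseline HbA1c is a strong predictor of reaching <7.0%.* The threshold arithmetic makes prediction plausible, but the protocol does not quantify it.
- *That the gain costs nothing.* It costs some complexity and a model-based p-value.
- *That the exploratory responder endpoints share the problem.* Section 8.5.3 does say "For categorical variables, a CMH test, stratified by baseline HbA1c stratum", but it leaves the detailed exploratory methods to the SAP. Only <7.0% was simulated, and baseline relates differently to a reduction of >=1.0%.
- *That taking the stratum from Visit 2 is a flaw.* Section 3.5 defines it openly as the value available at randomization. Analysing by the stratum used to randomize is normal practice, and the primary model does the same.

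**Conclusion.** The point holds as a minor efficiency improvement for one endpoint, HbA1c <7.0% at Week 28. The specified CMH test is valid. Adding continuous baseline HbA1c gains about 0.5 to 5 percentage points of power per comparison at two-sided 0.05, typically about 2, and close to nothing when baseline predicts the Week 28 value weakly.

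The size rests on assumed baseline distributions, slopes and mean change, on complete data, and on the protocol's 0.35% difference and 1.1% SD. The direction was the same in every scenario for the standardized analysis. For plain logistic regression it was the same except where baseline predicts weakly: about -0.2 points in one weak scenario at 0.05, and -0.8 at 0.05/13. The gain does not depend on including region.

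**What to change.** Before unblinding, prespecify for HbA1c <7.0% at Week 28 a logistic model with treatment, HbA1c stratum and continuous baseline HbA1c. Report the standardized (marginal) risk difference for each of the two comparisons, with a 95% CI and p-value from a robust SE with a small-sample correction. State that this p-value enters the multiplicity procedure, and keep the stratified CMH test as supportive. Because section 8.5.2 names CMH, the protocol wording and the SAP must be brought into agreement.

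Region can be left out. The weight-loss responder endpoint is outside this point and can stay with CMH.

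The cost is a change of wording and a few lines of code, with no new data. The downside is a model-based p-value and a slightly more complex analysis to explain.

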8.5.3 Analysis of exploratory variables

For categorical variables, a CMH test, stratified by baseline HbA1c stratum ($<9.0\%$ or $\geq 9.0\%$) will be applied to compare the differences between treatment groups.

For continuous variables, a MMRM or analysis of co-variance (ANCOVA) model will be applied to compare the differences between treatment groups.

Detailed analysis methodology for the exploratory efficacy endpoints will be provided in the SAP.

8.5.4 Analysis of PK variables

Plasma concentration data will be listed, summarized, and plotted vs time relative to intake of exenatide and dapagliflozin. A population PK analysis of data may be performed as outlined in a population PK analysis plan.

8.5.5 Safety and tolerability analysis

All safety and tolerability variables (including AEs, laboratory parameters, vital signs) will be summarized descriptively for each treatment group for the Safety population. Safety data collected prior to and after the patient initiates glycemic rescue therapy will be summarized together, as the patients are still on study medication after initiating the rescue therapy. Details on the safety analyses will be provided in the SAP.

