1.2 Rationale for study design, doses and control groups

This study will compare the dual combination of exenatide and dapagliflozin with each individual component in patients with T2DM who are inadequately controlled on metformin monotherapy. Because most diabetes agents reduce HbA1c by an average of 0.5 to 1.5%, many patients with T2DM and poor glycemic control are unlikely to reach HbA1c targets with a single agent alone. In the standard treatment paradigm, patients with poor glycemic control are prescribed oral agents sequentially, a process that results in significant delays in achieving optimal treatment. Combination insulin therapy is also an effective option in patients with very poor glycemic control, though at the cost of weight gain and hypoglycemia. Simultaneous administration of 2 effective glycemic-lowering agents that do not intrinsically increase weight or hypo glycemia is a potential alternative to sequential oral agent administration or insulin in patients with T2DM and poor glycemic control.

The combination of dapagliflozin and exenatide is expected to have additive glucose- and weight-lowering effects due to complimentary mechanisms of action. Dapagliflozin reduces plasma glucose and body weight in an insulin-independent fashion by causing excretion of urinary glucose and associated calories, whereas exenatide reduces glucose in an insulin-dependent fashion by stimulating insulin secretion, inhibiting glucagon release, delaying gastric emptying and promoting satiety via gastrointestinal (GI) and central mechanisms. Both agents act via a glucose-dependent mechanism and do not intrinsically increase the risk of hypoglycemia. The combination of the 2 drugs is thus expected to result in substantial HbA1c lowering, thus potentially decreasing the time to achieving glycemic targets in patients with very high HbA1c values while reducing the risks of weight gain or hypoglycemia.

Study design and regulatory requirement

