6.3.8 Hypoglycemia

Patients will be asked to test their blood glucose if they develop symptoms suggestive of hypoglycemia and to record specific symptoms in the patient diary. If the investigator determines that a patient experienced symptoms consistent with hypoglycemia, the event should be documented in the patient's source documentation and the hypoglycemia eCRF page (not AE eCRF page) must be completed. If a plasma or capillary glucose value of ≤ 70 mg/dL (3.9 mmol/L) is noted within the data, and the patient is asymptomatic, the investigator should assess whether the circumstances around the value are consistent with hypoglycemia. If the assessment is that the value is consistent with hypoglycemia, the hypoglycemia eCRF page should be completed. Study site personnel must obtain accurate information for the patient's file and for the hypoglycemia page of the eCRF. If the hypoglycemic episode intensity is judged to be severe, the investigator is required to contact the Sponsor.

The criteria for evaluating the intensity of a hypoglycemic episode are the following:

- MILD: Usually transient, requires no special treatment, and does not interfere with the patient's daily activities.
- MODERATE: Usually causes a low level of inconvenience or concern to the patient and may interfere with daily activities, but is usually ameliorated by simple therapeutic measures.
- SEVERE: Requires the assistance of another person to actively administer carbohydrate, glucagon, or other resuscitative actions. These episodes may be associated with sufficient neuroglycopenia to induce seizure or coma.

All hypoglycemia events will be programmatically classified as major, minor, or other hypoglycemia:

- Major hypoglycemia is an event that results in loss of consciousness, seizure or coma (or other mental status change consistent with neuroglycopenia in the judgment of the investigator or physician), which resolves after administration of glucagon or glucose. In addition, any event that requires third party assistance to resolve because of severe impairment in consciousness or behavior (whether or not symptoms of hypoglycemia are detected by patient) and is associated with a plasma or capillary glucose concentration of < 3 mmol/L (54 mg/dL) will be classified as major hypoglycemia.

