7.7.2 Rescue therapy

Patients who require rescue therapy (ie, FPG rescue criteria met) will receive open-label titrated basal insulin, as prescribed by the investigator (see Section 4.2). Patients should continue receiving study medication while receiving rescue therapy. Patients must first complete the Rescue visit procedures before receiving open-label rescue therapy.

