8.5.5.1 Adverse events

AEs will be coded using the Medical Dictionary for Regulatory Activities (MedDRA). All AEs will be summarized by treatment group. The number and percentages of patients who experienced at least 1 AE will be summarized by system organ class and preferred term. AEs will also be summarized by relationship to the study medication and by severity. Deaths, SAEs, and AEs leading to study discontinuation will be tabulated and presented in data listings. Patient level data listings of all AEs will be presented.

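### Safety data before and after insulin rescue are only pooled, so the hypoglycemia summary needs an exposure-adjusted pre-rescue counterpart

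*Protocol*

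**What the plan says.** Section 8.5.5 covers every safety variable: "All safety and tolerability variables (including AEs, laboratory parameters, vital signs) will be summarized descriptively for each treatment group for the Safety population". It then fixes how rescue is handled: "Safety data collected prior to and after the patient initiates glycemic rescue therapy will be summarized together", with the reason "as the patients are still on study medication after initiating the rescue therapy". It closes with "Details on the safety analyses will be provided in the SAP". The synopsis repeats the pooling rule and its reason.

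Rescued patients "will receive open-label titrated basal insulin" (Section 7.7.2) and continue blinded study drug. Rescue depends on glycemic criteria:

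- Table 3 (Section 4.2): confirmed FPG above 270 mg/dL from Week 8, above 240 from Week 12, and above 200 from Week 20 to the day before Week 36.
- Table 4 (Section 4.3): HbA1c above 8.0% from Week 36 to the day before Week 65.
- Table 5 (Section 4.4): HbA1c above 7.5% from Week 65 to the day before Week 91, then above 7.0% to the day before Week 104.

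Hypoglycemia has its own eCRF page, and "All hypoglycemia events will be programmatically classified as major, minor, or other hypoglycemia" (Section 6.3.8). No section exempts it from pooling or splits it by rescue. Section 1.2 says that both study agents "do not intrinsically increase the risk of hypoglycemia", and it names hypoglycemia as a cost of insulin therapy. For efficacy, Section 8.5.1 removes HbA1c values after rescue from the primary model.

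On discontinuations, Section 8.5.5.1 says "Deaths, SAEs, and AEs leading to study discontinuation will be tabulated". Section 3.9.1 keeps patients who stop study drug in follow-up, by telephone and at visits at Weeks 28, 52 and 104. Section 6.3.3 records, for every AE, what was done with the investigational product.

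**The concern.** Staying on study drug is a good reason to collect and report post-rescue safety data. It does not deal with the second drug that rescue adds. By the protocol's own account, insulin is a separate cause of hypoglycemia and the study agents are not intrinsic causes. Once a patient is rescued, an event can no longer be credited to the assigned treatment alone.

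The confounding has an expected direction. Glycemia decides who gets insulin, and the trial's hypothesis is that glycemia is better on the combination. If so, insulin goes more often to the monotherapy arms and raises their pooled hypoglycemia figures more. The combination then looks relatively safer than it is, or a real excess on it is hidden. The whole-period analyses at 52 and 104 weeks (Section 8.5.7) take in progressively tighter rescue thresholds.

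A smaller wording problem sits in Section 8.5.5.1. Read literally, a table of AEs leading to study discontinuation leaves out AEs that stopped study drug in patients who remain in follow-up.

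**Working it through.** **The plan's own figure.** Section 8.2 gives a difference of 0.35% HbA1c, SD 1.1%, 90% power and a 0.05 level (two-sided in Section 8.5.1).

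- Normal approximation: n = 2 × (1.960 + 1.282)² × 1.1² / 0.35² = 207.6, so 208 per group.
- Exact t-test: 209 per group (power 0.9006), as stated.
- 209 / 0.95 = 220 per group. 660 / 0.6 = 1100 screened.

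The sample size is not in dispute. Its 0.35% and 1.1% are reused below.

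**Step 1: does the hypothesis imply unequal rescue?** Share above a threshold = 1 − Φ((threshold − mean) / 1.1), with the combination mean 0.35 lower. Assumptions: normal HbA1c and a monotherapy mean between 7.0% and 8.0%.

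| Threshold | Monotherapy | Combination |
|---|---|---|
| >8.0% | 18–50% | 11–38% |
| >7.5% | 33–68% | 22–55% |
| >7.0% | 50–82% | 38–72% |

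At matching means the gap is 7 to 13 percentage points. Example for a mean of 7.0% and threshold 8.0%: 18.2% − 11.0% = 7.2 points. These are shares eligible at one threshold, not predicted rescue rates.

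**Step 2: shift when pre-rescue risk is equal.** Pooled proportion in an arm = h0 × (1 − r) + h1 × r, where r is the share rescued, h0 the risk without insulin and h1 the risk in rescued patients. With h0 and h1 the same in both arms, the spurious difference is (r_mono − r_comb) × (h1 − h0). The documents give none of these rates. Assumed: h0 = 2%; h1 = 5%, 10% or 20%.

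| Rescue, combination vs monotherapy | h1 = 5% | h1 = 10% | h1 = 20% |
|---|---|---|---|
| 2% vs 5% | 0.09 | 0.24 | 0.54 |
| 5% vs 15% | 0.30 | 0.80 | 1.80 |
| 22% vs 32.5% | 0.32 | 0.84 | 1.89 |
| 55% vs 67.5% | 0.37 | 1.00 | 2.25 |

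Entries are percentage points in favor of the combination, where the true difference is zero. The range is 0.1 to 2.3 points. With 220 per arm the largest is 0.0225 × 220, about 5 patients.

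**Step 3: can pooling hide a true excess?** Take a pre-rescue risk of 4% on the combination and 2% on monotherapy, with the same h1 in both arms once rescued.

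- Rescue 5% vs 15%, h1 = 10%: (0.04 × 0.95 + 0.10 × 0.05) − (0.02 × 0.85 + 0.10 × 0.15) = 4.3% − 3.2% = 1.1 points.
- Same rescue, h1 = 20%: 4.8% − 4.7% = 0.1 points.
- Rescue 22% vs 32.5%, h1 = 20%: 7.52% − 7.85% = −0.3 points.

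If instead the 2-point excess persists after rescue, the pooled difference is 2 − (r_mono − r_comb) × (h1 − 2%), with h1 the monotherapy value. The same cases give 2 − 0.8 = 1.2, 2 − 1.8 = 0.2 and 2 − 1.9 = 0.1 points. So the shrinkage does not depend on the equal-h1 assumption, but the reversal does.

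**The case against.** - **The SAP may already handle it.** Section 8.5.5 leaves the details to the SAP, which is not shown. A reader might infer that the protocol rules out a pre-rescue table or that none exists; the text supports neither. What stands is that the protocol itself makes the pooling choice for all safety variables and makes no exception for hypoglycemia.
- **Hypoglycemia is not prominent in the safety plan.** A reader might take low hypoglycemia risk to be a stated safety objective. Section 2.4 lists AEs, laboratory tests, physical examination and vital signs and does not name it, and safety is descriptive. It still belongs to the safety variables covered by 8.5.5, and Section 1.2 makes it part of the rationale.
- **More insulin in the monotherapy arms is an inference.** It should not be read as fact. It follows only if the combination works, because no rescue rates are given.
- **The effect may be small.** To Week 28, rescue needs a repeated high FPG and cannot start before Week 8. The >7.0% criterion applies only from Week 91, leaving at most about 13 weeks of treatment after it. The formula ignores time on insulin. These points support a small effect to Week 28 and caution about the upper range.
- **A pre-rescue summary has its own bias.** It stops at a post-randomization event and shortens observation more in the arms rescued more. Crude pre-rescue proportions could then undercount monotherapy events. This stands, and it is why such a summary should be exposure-adjusted and should not replace the pooled one. Pooling answers a legitimate question about the assigned strategy including rescue.
- **Body weight.** A reader might extend the point to insulin-related weight gain. The documents do not support that: weight is a secondary efficacy endpoint (Section 8.4.2) and is not governed by the safety pooling sentence.
- **Discontinuation wording.** The protocol uses the terms loosely: for the same liver criteria, Section 3.9 refers to stopping study medication and Appendix C to leaving the study. All AEs are also summarized and listed. It is therefore too strong to say that these events would be lost; this is a wording correction.

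**Conclusion.** The point holds in limited form. Pooling is a defensible rule for safety data in general, but the stated reason does not cover hypoglycemia, where rescue adds an agent that the protocol itself regards as a cause. As the only summary, the pooled one would tend to favor the combination if its glycemic advantage is real, and it could shrink a true excess.

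The size cannot be known from the documents. With an assumed 2% risk off insulin, 5–20% in rescued patients and rescue gaps of 3 to 12.5 points, the shift is about 0.1 to 2.3 percentage points when pre-rescue risk is equal. It is probably small to Week 28 and larger in the extensions. No hypothesis test is affected, and nothing here bears on the rescue criteria themselves. The change is worth making because it is cheap and hypoglycemia figures will be read across arms. The discontinuation wording in 8.5.5.1 is a separate, minor correction.

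**What to change.** In Section 8.5.5 and the synopsis, keep the pooled summary for all safety data. Add a hypoglycemia summary (major, minor, other) that excludes events on or after the start of rescue, with exposure-adjusted rates: events or patients per pre-rescue patient-year. Present it next to the pooled summary, and state that it is the one to use when attributing hypoglycemia to the study drugs.

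In Section 8.5.5.1, tabulate AEs leading to discontinuation of study medication, derived from the action on investigational product already recorded under 6.3.3, in addition to those leading to withdrawal from the study.

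The cost is one extra hypoglycemia table set, one AE table from existing data and a few sentences. The pre-rescue summary has less exposure and ends at a post-randomization event, and both limits should be stated with it.
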